Age-related perceptual and cognitive declines are associated with difficulties performing everyday tasks required to remain independent [1]. Encouraging improvements in cognitive abilities have been shown for a variety of short-term interventions such as group and individual training on abilities (e.g., the ACTIVE trial; [46]), digital games [6, 23], aerobic exercise [26], and combined treatments [5]). The rationale for these interventions is that they can be expected to support the maintenance of functional independence in older adulthood given the relatively strong relationship between Instrumental Activities of Daily Living (IADLs) performance and cognitive abilities [1], and the range of IADLs required for independence.

There are, however, several limitations to the design and interpretation of broad ability-level cognitive training described above [43]. First, over a century of research on skill acquisition has shown relatively narrow transfer and strong domain specificity for acquired skills [20]. In fact, sometimes a narrow training package may be more effective than training of general abilities, namely broad training, depending on the type of task and target outcome [33]. Given the range of interventions that have shown some efficacy, application of this knowledge to deploying cost-effective population-level interventions requires assessing their *comparative effectiveness*.

Second, relatively few intervention studies have assessed independence using metrics other than cognitive ability measure proxies. For example, many studies have used laboratory task outcomes such as the Useful Field of View (UFOV) test - as a predictor of driving crashes [22] - rather than using performance data from real or simulated driving. Third, practice effects on cognitive measures that are repeated from baseline to post-training test can make it difficult to estimate true change, although increased participant age tends to minimize practice effects and alternate form use can almost eliminate practice effects for some tests [11], though not for all tasks during relatively long periods of intervention [e.g., 37, 38, 39]. Finally, placebo effects, particularly expectation effects, are a serious threat to interpreting intervention studies [8].

[figure not shown]

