This randomized trial was designed to compare the effectiveness of broad and directed (narrow) technology-based training on basic perceptual and cognitive abilities in older adults and on the performance of simulated tasks of daily living. Participants were randomly assigned to four training conditions: (1) a brain game; (2) a video game; (3) IADL training for both fraud avoidance and driving; or (4) an active control condition, involving puzzle solving. This trial seeks to provide guidance not just about what works, but also what works best for a given investment (i.e., time, money) in older adults. The current trial was specifically designed to

address the several methodological limitations mentioned above, including: (1) the development of direct measures of IADL performance, targeting areas related to risks for catastrophic failure (e.g., crashes in driving, losing financial resources to fraud); (2) the use of alternate forms to provide more precise estimates of treatment effects (for both cognitive and IADL measures); (3) inclusion of an active control condition; and (4) measurement of expectation effects (as recommended in [43]). In this paper, we provide a primer to the design of this trial and describe the baseline characteristics of our sample.

Overall design

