#### **EVALUATION OF RANDOM ASSIGNMENT**

1. We plan to compare the 4 arms at baseline on the variables of age, education level, and gender and on the primary and secondary outcome variables (MANOVA across variables) to assess if random assignment resulted in equivalence across groups. If it did not, then we plan to use ANCOVAs in the next stage rather than ANOVAs, controlling for baseline differences on these variables.

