#### **EFFICACY ANALYSES FOR PRIMARY & SECONDARY OUTCOME VARIABLES**

Analyses Immediately following training

1. We plan 4 arms (Brain HQ, Rise of Nations, Driving and Fraud Avoidance Training, Puzzle Solving) x 2 times of measurement (baseline, post-training) ANOVAs (or ANCOVAs) for the following primary variables: fraud detection accuracy score, Driving Hazard Perception Test (safety and accuracy of navigation), Self-reported IADL task, Speed of Processing.

2. We plan 4 arms (Brain HQ, Rise of Nations, Driving and Fraud Avoidance Training, Puzzle Solving) x 2 times of measurement (baseline, post-training) ANOVAs (or ANCOVAs) for the following secondary variables: Technology Proficiency (CPQ & MDPQ average z-scored variables), Numeracy (accuracy on Berlin Numeracy Test), Reasoning Ability (average z-scored variables for Letter Sets & Ravens), Memory Ability (Average z-scored variables for Hopkins Verbal Learning Test and Rey Auditory Verbal Learning Test), Miami IADL task.

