#### Analyses following one-year follow-up

3. We plan 4 arms (Brain HQ, Rise of Nations, Driving and Fraud Avoidance Training, Puzzle Solving) x 2 times of measurement (baseline, 1-year follow-up) ANOVAs (or ANCOVAs) for the following primary variables: fraud detection accuracy score, Driving Hazard Perception Test (safety and accuracy of navigation), Self-reported IADL task, Speed of Processing, Knowledge about Driving (accuracy), Knowledge about Finances and Fraud (accuracy).

4. We plan 4 arms (Brain HQ, Rise of Nations, Driving and Fraud Avoidance Training, Puzzle Solving) x 2 times of measurement (baseline, 1-year follow-up) ANOVAs (or ANCOVAs) for the following secondary variables: Technology Proficiency (CPQ & MDPQ average z-scored variables), Numeracy (accuracy on Berlin Numeracy Test), Reasoning Ability (average z-scored variables for Letter Sets & Ravens), Memory Ability (Average z-scored variables for Hopkins Verbal Learning and Rey Auditory Verbal Learning Test), Miami IADL task.

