### COMPARATIVE EFFECTIVENESS ANALYSES

#### Analyses immediately following training

1. Immediate gain scores (post-training - baseline)/hours of reported training, for above primary and secondary variables will be compared across Arms.

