#### Analyses following one-year follow-up

2. Long-term gain scores (1-year follow-up - baseline)/hours of reported training, for above primary and secondary variables will be compared across Arms.

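### Alternate test forms are meant to sharpen the treatment estimates, but no planned analysis has a form term or equates the forms, which costs precision if form order varied between participants

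*Protocol*

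**What the plan says.** In the paragraph that closes its introduction, just before the Overall design heading, the Protocol lists as one of four methodological improvements "the use of alternate forms to provide more precise estimates of treatment effects (for both cognitive and IADL measures". The reason comes slightly earlier, where practice effects are named as a weakness of previous studies and the text notes that "alternate form use can almost eliminate practice effects for some tests".

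The SAP's efficacy section plans four arms "x 2 times of measurement (baseline, post-training) ANOVAs (or ANCOVAs) for the following primary variables", and the same for the secondary variables. The one-year section plans four arms "x 2 times of measurement (baseline, 1-year follow-up) ANOVAs (or ANCOVAs) for the following primary variables", again with a parallel item for the secondary variables.

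The ANCOVA version is triggered by a baseline comparison of the arms on the "variables of age, education level, and gender and on the primary and secondary outcome variables". If the arms are not equivalent, "then we plan to use ANCOVAs in the next stage rather than ANOVAs, controlling for baseline differences on these variables". Form is not among these variables.

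The comparative effectiveness section uses "Immediate gain scores (post-training - baseline)/hours of reported training" and "Long-term gain scores (1-year follow-up - baseline)/hours of reported training". The exploratory regressions use age, education, gender, occupation, expectation and arm. Some composites are averages of z-scores, but the SAP does not say whether standardisation is within form, within visit or pooled. The Blom transformation is equally silent on form.

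**The concern.** Alternate forms of a test are rarely of exactly equal difficulty. Using them removes some practice effect but adds a known source of variation: which form a person had at which visit. That variation can be removed if the analysis knows the form. A plan that relies on alternate forms for precision, but analyses the scores as though every form were the same, may give back part of what the forms were meant to buy.

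At stake is efficiency in the arm contrasts for those cognitive and IADL outcomes that have alternate forms. The readable text does not say which outcomes these are. A second, separate matter is how within-arm gains are to be read if every participant took the forms in the same order.

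**Working it through.** **Is form handled anywhere?** I went through every SAP section: random assignment, distributions, efficacy after training, efficacy at one year, comparative effectiveness and exploratory regressions. None has a form or form-order term, equating, or standardisation stated to be within form. The plan gives no figure on this point to reproduce.

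**Inputs.** All are assumptions, because the documents give no standard deviation, retest correlation, form gap, sample size or power:
- outcome SD = 1 at each visit
- retest correlation r = 0.6 to 0.8
- two forms differing in mean difficulty by d SD, with d = 0.1 to 0.5
- for the simulation: 60 per arm, r = 0.7, true arm effect 0.4 SD, two-sided 5% test, 4,000 runs

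**Case 1: order varies, half A-then-B and half B-then-A within each arm.** With two visits, the arm-by-time test is a comparison of change scores between arms. Each change score is the arm's change, plus or minus d, plus error.

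- Variance of change with form order in the model: 2(1−r)
- Variance of change without it: 2(1−r) + d²
- Inflation: d²/(2(1−r))

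| d | r = 0.6 | r = 0.7 | r = 0.8 |
|---|---|---|---|
| 0.1 | 0.01/0.8 = 1.25% | 0.01/0.6 = 1.7% | 0.01/0.4 = 2.5% |
| 0.2 | 0.04/0.8 = 5% | 0.04/0.6 = 6.7% | 0.04/0.4 = 10% |
| 0.3 | 0.09/0.8 = 11.3% | 0.09/0.6 = 15% | 0.09/0.4 = 22.5% |
| 0.5 | 0.25/0.8 = 31.3% | 0.25/0.6 = 41.7% | 0.25/0.4 = 62.5% |

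The equivalent loss of participants is 1 − 1/(1 + inflation). For r = 0.6 to 0.8 that is about 1–2% at d = 0.1, 5–9% at d = 0.2 and 10–18% at d = 0.3.

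The simulation agrees. At d = 0.3 the standard error of an arm contrast is 0.152 without a form-order term and 0.141 with it, and power is 0.76 against 0.80. At d = 0.5 the standard errors are 0.169 and 0.141, and power is 0.68 against 0.80. The mean estimate is 0.40 for a true 0.40, so omitting the term does not bias the contrast.

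**Case 2: everyone takes the forms in the same order.** Every change score contains the same d, which cancels between arms. In the simulation at d = 0.3 the arm-by-time contrast keeps its mean (0.40) and its standard error (0.141). The change in the control arm, truly zero, is estimated at 0.297, so form difficulty is read as gain over time.

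**A consequence for gain per hour in Case 2.** This measure divides a raw gain by reported hours, so a constant shift d becomes d/hours and cancels only if hours are alike across arms. The Protocol's recruitment script gives about 20 hours. The IADL training script's pace of 30–60 minutes on 4–5 days for 4 weeks spans 0.5×4×4 = 8 to 1×5×4 = 20 hours. At d = 0.3, the spurious difference between 8 and 20 hours is 0.3/8 − 0.3/20 = 0.0225 SD per hour, and between 16 and 20 hours it is 0.3/16 − 0.3/20 = 0.004. The same script's course lengths (about 6 hours and up to 5–6 hours, each taken twice) suggest about 22–24 hours, which would reverse the sign. Neither size nor direction can be settled from the documents.

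**The case against.** The strongest reply is that the harm depends on facts that cannot be seen. The Protocol's Battery and Randomization Procedures headings have no readable text, so the tests concerned, the number of forms and the assignment scheme are unknown. The forms may be nearly parallel, in which case the loss is a percent or two. Standardisation within form, if that is what the z-scored composites use, would already remove the mean difference. The formula is for a single two-form test and does not carry over unchanged to two-test composites or to an ANCOVA on baseline. All of this stands, and it is why the sizes are illustrative and the missing scheme is not counted as a fault.

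Three stronger readings are tempting but not supported.

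- A reader might infer that alternate forms cannot improve precision, because practice is common to all arms. Only the mean practice effect cancels. Variation in practice between people stays in the error, and practice that differs by arm would bias the contrast. Alternate forms can reduce both.
- A reader might infer that the models fail whichever way forms were assigned. With a fixed order the arm-by-time contrast is untouched, as Case 2 shows.
- A reader might infer that form assignment should be changed for participants still to be tested. If order was fixed, varying it brings no gain to the arm contrast, and it would tie the scheme to calendar time. It may also be too late: the Protocol describes randomisation in the past tense and refers to the sample's baseline characteristics.

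What the reply does not answer is that, where order varied, a model with form is better than the stated one and uses information that the test record should hold.

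**Conclusion.** The point holds as a cheap improvement to the analysis model. No bias in the arm-by-time contrast and no type I error problem is claimed.

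If form order varied between participants independently of arm, leaving form out inflates the error variance of change by d²/(2(1−r)) for a single two-form test with balanced order: negligible for nearly parallel forms, and 11–23% at d = 0.3 with r = 0.6 to 0.8. If order was the same for everyone, the planned arm contrasts lose nothing. The limitation then lies in time effects and raw gains, and in anything computed from raw gains. It would go too far to say that particular outcomes do lose precision: that requires varying order, unequated scores and a non-trivial form gap, none of which the readable text establishes.

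**What to change.** State in the SAP which outcomes use alternate forms, how many forms each has, and how forms were assigned to visits. Then:

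1. **Where order varied between participants**, add form at each visit, or form order, as a factor in the efficacy ANOVAs or ANCOVAs, the gain-per-hour comparisons and the exploratory regressions. Keep arm as the treatment test. Alternatively, equate or z-score within form, pooled over arms, before computing change. For gain per hour this second route is cleaner, because dividing by hours makes the form shift differ from person to person.
2. **Where order was the same for everyone**, a form term cannot be separated from visit. State that time effects and within-arm gains include form difficulty, and read gain per hour with that caution if hours differ between arms.

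The cost is a form identifier from the test record and a few degrees of freedom per outcome: about one with two forms, two for a form main effect with three forms, and up to five if all six ordered pairs of three forms are distinguished. If the forms prove nearly parallel, the gain will be small.

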IADL1 Training Protocol

SPEAKING: The Center for Research and Education on Aging and Technology Enhancement (CREATE) is conducting a study on cognitive training. This study seeks to measure the possible benefits of brain training games and other types of training on the performance of cognitive tests and everyday tasks such as driving and finance management. For this study, we want you to complete the two different online education courses:

- 1.) AARP driver safety course
- 2) And the finances and fraud online education.

The AARP Driver Safety Course is designed to refresh your driving skills and your knowledge of the rules and hazards of the road. The finances and fraud online education is designed to help you learn how to manage your finances and protect yourself from financial fraud. You need to complete each course one at a time at your own pace and **we want you to complete each course twice** within the next 4 weeks (before the second lab visit).

025167

We expect that you will be able to complete each course twice within the next 4 weeks if you spend around 30-60 mins per day, for 4-5 days a week. The detailed training schedule will be provided at the end of today with take-home manual.

Wifi Setup

DEMONSTRATE: In this study, you will need to be able to connect to a wireless network. We will show you how to connect to a wireless network here, and you will need to follow these same steps at home. If you already have a wireless network at home, that's great. If not, we will provide you with a device that will provide you with wireless network for the length of the study.

*If participant does not have internet please refer to [MiFi Device Instructions](#) on page 4.

1. First click on the wireless network icon in the bottom right corner of the desktop. This will pull up a list of wireless networks. (*show where to click to pull up network list.*)
 1. For your training session, we will use the network **FSU_SECURE** to train you on how to login to a wireless network.
 1. Click **FSU_SECURE** from the list of wireless networks.
 1. Click the connect button.
 1. In the password prompt enter the password **CREATE2017**.
 1. Click the OK button.
 1. The computer will now connect to the wireless network.
 1. This is how you will connect to your wireless network at home or to your Mifi device.

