1. First click on the log in button at the top right of the AARP website.
 1. This is the login window. Here you will enter the email address and password that we setup when we purchased the AARP account for you.
 1. The email address and password is located on the laptop, right here.
 1. Now enter that login and password into the website to login.
 1. Then click the "Log In" button.

Participant Complete Acct Info

SPEAKING: Before you start the course, you will need to create your own account by entering additional information. Let's do that together now.

1. Please fill out information requested on the screen. You will need your driver's license number.
 1. **(Make sure the default email address is not changed)**

GUIDE PARTICIPANT: You won't be asked to enter the information again the next time you log in. From now on you will just need to type the email address and password to start training and click "Log in."

ASK: Do you have any questions before we continue?

My Account Page

GUIDE PARTICIPANT: This is your training summary for the course. This will provide information on how much of the training you have completed. It will also tell you that how many days left to complete, but please disregard that information (Days Left to Complete). Regardless of that information, as mentioned above, you just need to **complete both courses twice** (AARP Driver Safety Course and Finances & Fraud Education) within 4 weeks. This driver safety course will take around 6 hours to complete.

Start Course & Menu

GUIDE PARTICIPANT: Let's start the course now and go over it together.

1. Click the "CONTINUE TO COURSE" button to start the training session.
 1. A new popup window will appear and the course will automatically start, but I **am going to manually pause the video.**
 1. The course consists of several different units shown here in the menu. **(point at the Menu section).**
 1. Starting with the "Introduction" and ending with a final overview and assessment in "Unit 6: What Have We Learned".

1. You must always complete the units in order.

Navigating the Course

GUIDE PARTICIPANT: Now let's get into how to navigate the course.

1. You can pause or resume the course by clicking the play or pause button.
1. Click the "play" button at the bottom to resume the slide and then "pause" to stop the course.
1. You can move forward through the tutorial by clicking the "NEXT" button in the lower right corner after each slide (*point at the NEXT button*).

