1. You will also find a "BACK" button (*point at the Back button*) Use the "BACK" button if you want or need to go back one slide that you have already visited. Slides you have already visited will be indicated in a light grey.

Complete the "Introduction" Section

The Introduction section of the course (*point at Introduction in the Many bar*) presents a brief overview of the tutorial and more detailed instruction about how to navigate through the tutorial.

1. Now please go through the Introduction carefully, I will be here to help if you need it. You will learn how to use all the different buttons during the tutorial.
1. (*have participants go through the whole introduction. Don't leave while they complete the introduction – and when they finish, ask them to stop the course by clicking the pause button*).

AFTER COMPLETING INTRODUCTION: All right great. During your 4 weeks of at home training, we want you to spend roughly 30-60 minutes per day on this course. Never complete

more than 2 units per day or train more than 5 days a week. It's best to complete units as shown on page 2 of the take-home manual. We will go over this in more detail later. Do you have any questions?

Exiting the Course

SPEAKING: Now I want to show you how to close the course after you finish your session for the day. When you want to exit the course do the following:

1. Click on the “X” at the top right of the screen to close the course popup.
1. Then click on the “X” again to exit the browser completely.
1. This will close the AARP driver safety course page and pull up your diary.

Filling out Diary

DEMONSTRATE: The diary allows you to record your thoughts and feelings after each training session. With this diary, you will answer the following questions.

1. How **enjoyable, challenging, frustrating** you found the training that day.
 1. And how **motivated** you were in the training that day.
 1. Go ahead and answer those questions now for the introduction training you just completed.
 1. The next question asks “During today’s session, for how many minutes, did you stop to complete another task”. If you were interrupted or had to take a break from task, you would enter the number of minutes you stopped the task
 1. If you were not interrupted during your training session please click on the white box beneath the question and enter 0.

1. Enter the of number minutes you stopped to complete task. (*Help participant decide number*)

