 1. If you have any other comments on the task please write it in the comments section or enter “none”
 1. Enter your comments now.
 1. Once you have finished filling out your diary click the Save diary and Exit button.
 1. You will complete a diary after each training session.

Finances & Fraud Education

SPEAKING: Now I am going to give you a demonstration of how to access and start the second training course, **the finances and fraud education**. This course is structured very similar to the AARP driver’s safety course we just went over.

Open Task 2

DEMONSTRATE: The finances and fraud education is accessed by clicking the second task.

First, you will need to:

1. Click on the task 2 icon once at the top left of your desktop.
 1. This will bring you to the Finances and Fraud homepage.
 1. You should have your window in full screen while you complete the course.
 1. Click on the maximize button at the top right corner of the browser.

This finances and fraud education course will also take about or less than 5-6 hours to complete.

As you would do for the AARP driver’s safety course, we want you to spend roughly 30-60 minutes per day on this course. Never complete more than 2 units per day or train more than 5 days a week. It’s best to complete units as shown on page 2 of the take-home manual. We will go over this in more detail later. Do you have any questions?

Also please remember to only click on the Task 1 and Task 2 icons **once**, if you double click the icon it will pull up 2 windows and 2 diary pages.

Logging In

GUIDE PARTICIPANT: To access this course all you have to do is enter the password. The password is located on your laptop, it's "CREATE2017."

1. Enter CREATE2017 into the box designated password.
 1. Click "Login" to continue to the course.
 1. The course will automatically start, but **I am going to manually pause the video.**
 1. The course consists of several different units shown here in the menu. (*point at the Menu section*).
 1. Starting with the "Home" and ending with a final overview and assessment in "Unit 8".
 1. You must always complete the units in order.

Navigating the Course

GUIDE PARTICIPANT: Now let's get into how to navigate the course.

1. You can pause or resume the course by clicking the play or pause button.
 1. Click the "play" button at the bottom to resume the slide and then "pause" to stop the course.

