DEMONSTRATE: For the rest of today’s lab training session, we want you to resume the AARP driver’s safety course and complete **Unit 1**. This time you will try to start the AARP course based on what you just learned. I will be here to answer any questions you may have and help guide you through your training. But we also want you to attempt to use the take-home manual as practice for the time when you are alone at home and might have a question that the manual could answer. Let’s start the course when you’re ready.

(Watch if the participant can figure out how to get back to AARP and start Unit 1. Remind participants of that all the necessary information needed is described in the take-home manual and encourage them to use the manual from this point if they have questions, so that they can

also learn how to find information from it. If you have any questions, you can also refer to the take-home manual to guide participants.

(Once they finish the unit 1, ask them to stop the course and fill out the diary)

End of Lab Training Session

AFTER COMPLETING AARP UNIT 1 & Diary: Do you have any questions or anything that needs clarification before we end our training?

(Interventionist should answer any questions. Also please emphasize that we want them to complete each course twice and follow the training schedule attached in the manual. Especially, tell them they don't go to the last unit of each course – unit 6 for the AARP driver's course and unit 8 for Finances and Fraud course if it is "the first time". Please show them the training schedule!!!)

Control training (Crosswords, Sudoku, Word Search)

Call Scripts

One week call - CHECK IN

Hi, this is [your name] from the CREATE lab at FSU. Is _____ there? So, it's been a week since you were given a the laptop as part of your participation in the CE study and I'm just calling to check in and make sure you're not having any problems with [the condition] or with the laptop in general.

Setup appointment - POST

Hi, this is [your name] from the CREATE lab at FSU. Is _____ there? I was just calling to remind you of your two post testing days are [post testing days], and we ask that you bring in the

laptop and all other materials with you when you come in for those days. If you have any questions please call [contact]. Thank you.

Setup appointment - FOLLOW UP

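### The IADL script's 30-60 minutes on 4-5 days a week (8-20 h) is too little at its low end for both courses twice; about 60 minutes on 5 days fits the script's own course lengths

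*Protocol*

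**What the plan says.** All of the following is in the Protocol's script for the IADL arm, unless another place is named.

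- *IADL1 Training Protocol* sets the target of completing each course twice before the 4-week visit and says this is expected "if you spend around 30-60 mins per day, for 4-5 days a week". It adds "You need to complete each course one at a time at your own pace" and "The detailed training schedule will be provided at the end of today with take-home manual".
- *My Account Page*: "This driver safety course will take around 6 hours to complete".
- *Finances & Fraud Education, Open Task 2*: "This finances and fraud education course will also take about or less than 5-6 hours to complete".
- After the driver course introduction: "During your 4 weeks of at home training, we want you to spend roughly 30-60 minutes per day on this course". The same daily minutes are repeated for the fraud course. Both places add "Never complete more than 2 units per day or train more than 5 days a week".
- *End of Lab Training Session* has staff explain that participants do not "go to the last unit of each course" the first time through (Unit 6 for driving, Unit 8 for fraud). The driver Introduction, driver Unit 1 and the fraud Home section are done in the lab.

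Elsewhere in the Protocol, the recruitment telephone script describes roughly 20 h of training over a month. The Brain HQ and Rise of Nations materials ask for about an hour a day, 5 days a week. The SAP (*Comparative Effectiveness Analyses*) divides gain scores by reported training hours.

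**The concern.** A single spoken script gives both a training rate and the lengths of the courses, and the lower part of the rate does not fit the lengths. The IADL arm is the directed-training arm in the broad-versus-narrow comparison. A participant who paced by the low end of the spoken range could reach the post-training visit with the second pass unfinished.

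The range is also wider and lower than the hour a day, 5 days a week, asked of the Brain HQ and Rise of Nations arms. Because reported hours are the denominator in the SAP's gain-per-hour comparisons, uneven hours by arm should at least be visible to a reader.

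**Working it through.** **Stated time.** Hours over 4 weeks = minutes/60 × days per week × 4. The script gives only the rate; the totals follow from it.

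- 30 min × 4 days: 0.5 × 4 × 4 = 8 h
- 30 min × 5 days: 0.5 × 5 × 4 = 10 h
- 45 min × 4.5 days (midpoint): 0.75 × 4.5 × 4 = 13.5 h
- 60 min × 4 days: 1 × 4 × 4 = 16 h
- 60 min × 5 days: 1 × 5 × 4 = 20 h

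**Content before deductions.** Let F be the fraud course length in hours. Two passes of both take 2 × (6 + F), which is 22 h for F = 5 and 24 h for F = 6.

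**Home content after deductions.** Unit lengths are not given, so sections within a course are taken as equal, in two variants. F = 4 is added as an illustration, because the script sets no lower limit on the fraud course.

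- Variant A (Introduction and Home negligible; 6 driver and 8 fraud units). The first home pass is driver Units 2-5, 4 × 6/6 = 4 h, plus fraud Units 1-7, 7F/8.
- Variant B (Introduction and Home each a full section; 7 driver and 9 fraud sections). The first home pass is 4 × 6/7 = 3.43 h plus 7F/9.
- In both, the second pass is 6 + F if it takes as long as the first.

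| F | First pass A / B | Second pass | Total A / B | Min per day at 5 days, A / B |
|---|---|---|---|---|
| 6 h | 9.25 / 8.10 h | 12 h | 21.25 / 20.10 h | 63.8 / 60.3 |
| 5 h | 8.38 / 7.32 h | 11 h | 19.38 / 18.32 h | 58.1 / 55.0 |
| 4 h | 7.50 / 6.54 h | 10 h | 17.50 / 16.54 h | 52.5 / 49.6 |

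Minutes per day = total × 60/20, for 20 training days. So about 18-21 h remain for F = 5-6, and 16.5-17.5 h for F = 4. The driver course alone needs 4 + 6 = 10 h (A) or 3.43 + 6 = 9.43 h (B) at home with equal passes, which is more than 8 h.

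**Share covered, and how fast the repeat would have to be.** Share covered = stated hours / total, with equal passes. Break-even = (stated hours − first pass)/(6 + F), the second-pass length, as a fraction of its first length, at which the time is just enough.

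| Stated time | Share covered, F = 5-6 (F = 4) | Break-even second pass, F = 5-6 (F = 4) |
|---|---|---|
| 8 h | 38-44% (46-48%) | at most 6% (5-15%) |
| 10 h | 47-55% (57-60%) | 6-24% (25-35%) |
| 13.5 h | 64-74% (77-82%) | 35-56% (60-70%) |
| 16 h | 75-87% (91-97%) | 56-79% (85-95%) |
| 20 h | 94-109% (114-121%) | 90-99% at F = 6; no faster repeat needed at F = 5 or 4 |

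**How short the fraud course would have to be, with equal passes.** F = (hours − 10)/1.875 in A and (hours − 9.43)/1.778 in B. This gives 1.9-2.3 h for 13.5 h, 3.2-3.7 h for 16 h and 5.3-5.9 h for 20 h. For 8 h the result is negative in both variants.

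**Unit cap.** Home units are 4 + 7 on the first pass and 6 + 8 on the second, 25 in all (27 if the second-pass Introduction and Home are counted). The cap of 2 units a day over 16-20 days allows 32-40, so the cap is not the obstacle.

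**The case against.** The stated range contains a workable value: its top is 20 h, which equals the recruitment figure and lies within the 18-21 h needed. The rate is offered as an expectation, the courses are self-paced, and the fraud course has no stated minimum length. A repeat of familiar material may well be faster. Participants are told to complete both courses twice and are shown a unit-by-unit schedule whose content is not in the documents. Its absence from the documents cannot count against the plan.

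Most of this stands. It rules out three stronger readings that a reader might infer.

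- *The whole range is inadequate.* The 22-24 h before deductions suggests this, but it ignores the units skipped or done in the lab.
- *The middle of the range, or 60 minutes on 4 days, is shown to fail.* Those points fall short only if the repeat is about as long as the first pass and the fraud course is near 5-6 h. The script fixes neither.
- *The IADL arm was under-dosed, or the comparison is biased.* Nothing in the documents shows what participants did, and the direction of any effect on gain or on gain per hour is not determined.

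The objection does not rescue the low end. At 8-10 h the second pass would have to take no more than about a quarter of its first length, or about a third with a 4 h fraud course. Nor do the daily minutes stated for each course add up within a day, since the courses are taken one after the other.

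**Conclusion.** The point holds as an inconsistency in a dose instruction to one randomised arm. The low end, 8-10 h, covers about 38-55% of the home content with a 5-6 h fraud course and equal passes, and 46-60% with a 4 h fraud course. The shortfalls at 13.5 h and 16 h depend on the equal-pass and fraud-length assumptions. At 20 h the instruction is about right and agrees with the recruitment script and with the other two training arms whose scripts are given. All totals rest on equal section lengths within a course.

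The consequence is a risk that some IADL participants stop short of the second pass if they pace by the spoken minutes and not by the schedule. It is a minor point, worth making because the correction is cheap.

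**What to change.** In the three places where the IADL script gives daily minutes, say about 60 minutes per day, 5 days a week. Keep completion of both courses twice as the target, and check that the take-home schedule agrees.

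The cost is script wording and a check of the manual. The instruction becomes slightly more demanding for IADL participants. Sixty minutes is still marginal if the fraud course takes a full 6 h (60-64 minutes needed), which is why the completion target should stay.

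The Protocol describes randomisation in the past tense, so the wording change does not help anyone already trained. For them, report training hours by arm beside the IADL contrast, with course completion where it was recorded. Hours are already needed for the gain-per-hour analyses. The driver course account page shows progress, but the documents do not say whether it separates a second pass, so hours by arm is the firmer item.
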